**16.0 TERMINATION OF THE STUDY**

The PI may terminate the study at any time. The IRB and FDA also have the authority to terminate the study should it be deemed necessary. There is no planned interim analysis of this study and there are no early stopping rules in place for excessive toxicity. The study will be monitored by a designated DSMB which will meet every 6 months to review the protocol accrual and results including toxicity. The DSMB has the independent authority to terminate the study at their discretion. This information will be included in the consent form.

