## 10.0 DATA AND SAFETY MONITORING PLAN

The PI of the study will have primary responsibility for ensuring that the protocol is conducted as approved by the FHCRC Scientific Review Committee and Institutional Review Board. The PI will ensure that the monitoring plan is followed, that all data required for oversight of monitoring are accurately reported to the FHCRC/UW Cancer Consortium Data and Safety Monitoring Committee (DSMC), that all adverse events are reported according to the protocol guidelines, and that any adverse reactions reflecting patient safety concerns are appropriately reported. The PI or designee will personally review with the Research Nurse the clinical course of all the enrolled patients weekly. A delegation log of authority will be kept to delineate the role of co-investigators (**Appendix K**).

Under the provisions of the Institutional Data Safety and Monitoring Plan, the Cancer Consortium Clinical Research Support Office provides monitoring for Good Clinical Practice and compliance by qualified monitors unaffiliated with the conduct of the study. Monitoring visits are conducted in accordance with the Cancer Consortium Data and Safety Monitoring Plan.

This protocol will also be monitored by a dedicated DSMB on a semi-annual basis. Enrollment, response and toxicity data will be reviewed. The DSMB has the authority to terminate the study, hold enrollment, or suggest modifications to the protocol as indicated.

An annual review of the progress of the study with respect to the monitoring plan will be performed by the DSMC. The DSMC will review the number of subjects and unanticipated problems. The DSMC will also review DSMB reports regarding accrual, stopping rules, protocol adherence to the data and safety monitoring plan, as well as DSMB recommendations. If the DSMC finds a study to be continuing accrual in violation of the study design or the recommendation of the DSMB, the DSMC has the authority to suspend trial accrual.

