**15.0 STATISTICAL CONSIDERATIONS**

We estimate the rate of hematologic response to iron chelation with deferasirox to be 0.25 based on previously published studies in patients with MDS and iron overload. The null hypothesis that the true response rate is 0.05 will be tested against a one-sided alternative. The accrual goal is for a total of 25 patients. The null hypothesis will be rejected if 4 or more responses are observed in 25 patients. This design yields a type I error rate of 0.0336 and power of 0.9008 when the true response rate is 0.25. Descriptive statistics will be performed and the planned number of patients is estimated based on the patients we have that would meet eligibility criteria.

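### No futility criterion is prespecified for the DSMB's six-monthly response reviews, yet the error rates printed in Section 15 are those of a design that stops at 0 responses in the first 15 patients

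*Combined protocol and SAP*

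**What the plan says.** Section 15.0 describes a single-stage test. The null and alternative are given by "The null hypothesis that the true response rate is 0.05 will be tested against a one-sided alternative" and "We estimate the rate of hematologic response to iron chelation with deferasirox to be 0.25". The size and decision rule are "The accrual goal is for a total of 25 patients" and "The null hypothesis will be rejected if 4 or more responses are observed in 25 patients". The operating characteristics are stated as "This design yields a type I error rate of 0.0336 and power of 0.9008 when the true response rate is 0.25". No first stage is mentioned.

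Section 16.0 says: "There is no planned interim analysis of this study and there are no early stopping rules in place for excessive toxicity". It leaves termination to the discretion of the DSMB, with the PI, IRB and FDA also able to end the study.

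Section 10.0 has a dedicated DSMB meet semi-annually. Of its remit it says "Enrollment, response and toxicity data will be reviewed", and it gives the board power to terminate or to hold enrollment. The same section adds: "The DSMC will also review DSMB reports regarding accrual, stopping rules, protocol adherence". No stopping rule, for response or for toxicity, is defined in the document.

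Sections 4.2.1 and 12.1 place the primary endpoint, erythroid improvement by the modified IWG criteria, at 6 months. Section 7.7 says withdrawn patients are not replaced and the analysis is by intention to treat.

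**The concern.** The three sections do not fit together. Section 10 gives the DSMB the responder count twice a year and has a second committee review reports on stopping rules. Section 16 rules out an interim analysis. Section 15 prints error rates that its own rule does not produce.

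In practice, a run of non-responders triggers nothing that was written down in advance. Section 15 supplies the null rate, the target rate and the final cut-off, so the board is not without reference points. It has no agreed threshold at an intermediate sample size.

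The possibility of a low response rate is real. Section 15 takes 0.25 from patients with iron overload, whereas entry here requires a ferritin of only 100 ng/mL or more, and Section 2.2 acknowledges that data below 1000 ng/mL are sparse. If the true rate is near the null, later enrollees add little to the primary decision.

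**Working it through.** **Inputs.** From Section 15: null rate 0.05 (one-sided), alternative 0.25, n = 25, reject at 4 or more; stated type I error 0.0336 and power 0.9008. From Section 4.2.1: endpoint read at 6 months. The accrual rate is not given, so the values used in step 5 are assumptions.

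**1. The plan's own figures, single stage.** P(reject) = 1 − P(X ≤ 3), with X ~ Bin(25, p).
- p = 0.05: 1 − (0.27739 + 0.36499 + 0.23052 + 0.09302) = **0.0341**; stated 0.0336.
- p = 0.25: 1 − (0.00075 + 0.00627 + 0.02508 + 0.06411) = **0.9038**; stated 0.9008.

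Neither stated figure is reproduced.

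**2. The same rule with a stop at 0 responses in the first 15.** The only rejections lost are those with 0 of 15 followed by 4 or more of the last 10, so P(reject) = single-stage value − (1 − p)^15 × P(Bin(10, p) ≥ 4).
- p = 0.05: 0.95^15 = 0.4633 and P(Bin(10, 0.05) ≥ 4) = 0.00103; the product is 0.00048. 0.03409 − 0.00048 = **0.0336**.
- p = 0.25: 0.75^15 = 0.01336 and P(Bin(10, 0.25) ≥ 4) = 0.2241; the product is 0.0030. 0.9038 − 0.0030 = **0.9008**.

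Both printed figures are matched to four decimals.

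**3. Is the match unique?** A search took total n from 20 to 30, final cut-offs from 2 to 7, every first-stage size, and every futility cut-off below the final one. Only this rule matched both figures. The nearest others with n = 25 and a cut-off of 4 match the type I error but not the power:

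| Futility stop | Type I error | Power |
|---|---|---|
| 0 of 15 | 0.03361 | 0.90079 |
| ≤ 1 of 20 | 0.03364 | 0.90155 |
| ≤ 2 of 23 | 0.03355 | 0.90144 |

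**4. How often the stop triggers.** 46.3% of trials at a true rate of 0.05 and 1.3% at 0.25. It triggers more often if the drug does less: 0.98^15 = 74% at a true rate of 0.02.

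**5. Patients spared when it triggers.** At most 25 − 15 = 10. That maximum, and the matching expected size of 15 + 0.537 × 10 = 20.4 at a rate of 0.05, require enrollment to pause after patient 15 until all 15 are read. Without a pause and with a 6-month read, the number spared is max(0, 10 − 6a) at a patients per month:

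| Assumed accrual per month | Spared, decision at the read | Spared, after a further 6-month wait for the DSMB |
|---|---|---|
| 0.5 | 7 | 4 |
| 1 | 4 | 0 |
| about 1.7 or more | 0 | 0 |

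The last column is max(0, 10 − 12a). Averaged over all trials at a true rate of 0.05 (multiplying by 0.463), the saving is 1.9 to 3.2 patients at 0.5 per month and 0 to 1.9 at 1 per month.

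**The case against.** A single-stage trial of 25 with a discretionary DSMB is a legitimate design, and adding a stage could be called a preference. That would carry weight if Section 15 reported single-stage figures. It reports the two-stage ones, so some edit is needed in any case.

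Several stronger readings are tempting, and the documents do not support them:

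- *All 25 patients will be treated even if none of the first 15 responds.* Sections 10 and 16 let the DSMB terminate, and the PI, IRB and FDA may also do so. What is missing is a prespecified trigger.
- *Discretionary stopping leaves the error rates undefined.* Stopping for futility alone cannot raise the type I error above 0.0341. It can only lower power, and the DSMB would keep its discretion under the proposed rule too.
- *The rule protects against toxicity.* Section 16 does disclaim toxicity stopping rules, and Section 7.6 lists serious harms, but a response-based stop does not address them.
- *The rule saves 10 patients.* That is a ceiling which needs an accrual pause.
- *The protocol once contained this rule.* The numerical match invites the inference; nothing in the documents says so.

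It also stands that the last 10 patients inform the transfusion, ferritin, safety and marrow objectives, so their data would not be worthless after 0 of 15.

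**Conclusion.** The point holds as a gap and an inconsistency. Response is reviewed every 6 months with no prespecified futility criterion. Section 10 refers to stopping rules that are nowhere defined. Section 15's printed error rates are those of a 0-of-15 futility design that the protocol does not describe.

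The numerical mismatch is small: 0.0005 in type I error and 0.3 points in power. It does not change the 4-of-25 cut-off or make the trial unanalysable. The practical benefit of the rule ranges from nothing to 10 patients per stopped trial, depending on accrual speed and on whether enrollment pauses. The trigger probabilities assume independent responses at a common rate, with inactivity taken as a true rate of 0.05.

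**What to change.** Add to Sections 15 and 16, in substance: the DSMB will recommend closing accrual if none of the first 15 enrolled patients meets the primary endpoint (erythroid improvement at 6 months, as defined in Section 4.2.1 and Appendix G); otherwise accrual continues to 25 and the null is rejected at 4 or more responses. Amend the statement in Section 16 that no interim analysis is planned, so that Section 10's reference to stopping rules has something to point to. The printed 0.0336 and 0.9008 then stand.

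The text should also settle three details:
- whether accrual pauses after patient 15;
- that withdrawn patients stay in the 15, consistent with Section 7.7;
- how a response that has not yet lasted the 8 weeks required by Appendix G is counted at the look.

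The cost is a few sentences, using existing meetings and data, plus 0.3 points of power against the true single-stage value (none against the stated power) and a 1.3% chance of a wrong stop at a true rate of 0.25.

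If the sponsor prefers to keep one stage, Section 15 should instead state 0.0341 and 0.9038, and Section 10's mention of stopping rules should be reconciled with Section 16.

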## 8.0 GUIDELINES FOR ADVERSE EVENT REPORTING

### 8.1 Adverse Event Reporting/Institutional Policy

The following guidelines are the minimum Cancer Consortium IRB adverse event (AE) reporting guidelines. Protocol-specific additional reporting requirements for adverse events are addressed in Section 8.2.

In accordance with institutional policy, all adverse events which in the opinion of the PI are unexpected and related or possibly related to the research and serious or suggest that the research places research participants or others at greater risk of physical or psychological harm than was previously known or recognized be reported to the IRB within 10 calendar days of learning of the problem.

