#### Definitions:

**Adverse Event (AE)** - Any untoward medical occurrence in a patient or clinical investigation subject administered a pharmaceutical product, medical treatment or procedure and which does not necessarily have to have a causal relationship with this treatment. An adverse event can therefore be any unfavorable and unintended sign (including

an abnormal laboratory finding, for example), symptom, or disease temporally associated with the use of a medicinal product, medical treatment or procedure whether or not considered related to the medicinal product.

**Life-threatening AE** – Any adverse event that places the patient or subject, in view of the investigator, at immediate risk of death from the reaction.

**Unexpected AE** – An adverse event is “unexpected” when its nature (specificity), severity, or frequency are not consistent with (a) the known or foreseeable risk of adverse events associated with the research procedures described in the Protocol-related documents, such as the IRB-approved research protocol, informed consent document and other relevant sources of information such as product labeling and package inserts; and are also not consistent with (b) the characteristics of the subject population being studied including the expected natural progression of any underlying disease, disorder or condition any predisposing risk factor profile for the adverse event.

**Attribution** - The following are definitions for determining whether an adverse event is related to a medical product, treatment or procedure:

- An adverse event is “**related or possibly related to the research procedures**” if in the opinion of the PI, it was more likely than not caused by the research procedures.
- Adverse events that are solely caused by an underlying disease, disorder or condition of the subject or by other circumstances unrelated to either the research or any underlying disease, disorder or condition of the subject are not “related or possibly related.”
- If there is any question whether or not an adverse event is related or possibly related, the adverse event should be reported.

The Cancer Consortium Expedited Reporting Form should be completed for all adverse events that meet the expedited reporting requirements. The AE form (see **Appendix I**) should be faxed to the FHCRC Research Coordinator at [contact] within 10 business days of study staff awareness. All available information should be submitted.

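### Section 16 sets no toxicity stopping rule, and nothing supplied obliges a hold or an extra DSMB meeting between the 6-monthly ones: a trigger is a cheap safety improvement

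*Combined protocol and SAP*

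**What the plan says.** Section 16 is explicit: "There is no planned interim analysis of this study and there are no early stopping rules in place for excessive toxicity". It puts a DSMB in place that meets every 6 months and looks at toxicity: "The DSMB has the independent authority to terminate the study at their discretion". Section 10 adds: "The DSMB has the authority to terminate the study, hold enrollment, or suggest modifications to the protocol as indicated".

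The other safeguards are these:

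- **PI (Section 10).** "The PI or designee will personally review with the Research Nurse the clinical course of all the enrolled patients weekly".
- **SAEs (Section 9.2).** Every SAE goes to the PI and/or the study coordinator within 24 hours. The DSMB is not named as a recipient.
- **IRB (Sections 8.1 and 8.2).** An event that is unexpected, related and serious must "be reported to the IRB within 10 calendar days of learning of the problem". Section 8.2 leaves all other SAEs and deaths to the annual continuation report. Under the definitions in Section 8.1, an event can be unexpected because its "severity, or frequency are not consistent with (a) the known or foreseeable risk of adverse events". No number says when that point is reached.
- **DSMC (Section 10).** "The DSMC will also review DSMB reports regarding accrual, stopping rules, protocol adherence to the data and safety monitoring plan, as well as DSMB recommendations". Its stated ground for suspending accrual is a breach of the design or of a DSMB recommendation.
- **Institutional plan (Section 10).** "Monitoring visits are conducted in accordance with the Cancer Consortium Data and Safety Monitoring Plan". That plan is not among the supplied documents.

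Sections 7.6 and 7.7 govern dosing and withdrawal of the individual patient.

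**The concern.** Every route to a pause between DSMB meetings is discretionary. No number of toxic events, and no death, obliges anyone to hold enrolment or call the DSMB. The stopping rules that the DSMC is to review have no toxicity content in these documents.

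The clearest case is a related death from a toxicity that the protocol already lists. Fatal outcomes are described for renal failure (Section 7.6.3), hepatic injury (Section 7.6.6) and GI hemorrhage (Section 7.6.10). Such a death reaches the PI within 24 hours. If it is judged expected, it need not reach the IRB before the annual report, and no text requires it to reach the DSMB before its next meeting.

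This matters more here than in routine chelation. The target is ferritin below 100 ng/mL, entry starts at 100 ng/mL, and dosing is left to the treating clinician. Section 2.2 concedes that there is little clinical experience below 1000 ng/mL. At stake is whether an emerging excess of toxicity is reviewed promptly or only at the next scheduled meeting.

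**Working it through.** **1. Is there a plan figure to reproduce?** No. The documents state no toxicity limit and no grade 3 or higher rate. The only operating characteristics, in Section 15, concern the efficacy test. Section 2.4 gives creatinine increase in 37% of MDS patients, without grade.

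**2. Boundary.** Inputs: 25 patients (Section 15) and grade 3 or higher non-hematologic events, following the safety endpoint in Section 4.2.2. Assumption: an acceptable rate of 20%. The count k(n) is the smallest k with P(X ≥ k | n, 0.20) ≤ 0.10. For n = 5:

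- P(X ≥ 3) = 10(0.2³)(0.8²) + 5(0.2⁴)(0.8) + 0.2⁵ = 0.0512 + 0.0064 + 0.0003 = 0.058, so 3 qualifies.
- P(X ≥ 2) = 1 − 0.8⁵ − 5(0.2)(0.8⁴) = 0.263, so 2 does not.

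| First n treated | Count | Tail at 20% |
|---|---|---|
| 5 | 3 | 0.058 |
| 10 | 5 (4 would give 0.121) | 0.033 |
| 15 | 6 | 0.061 |
| 20 | 7 | 0.087 |

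**3. Chance that any count is reached.** This is an exact recursion that adds the first-crossing probability at each n. At a true 20% it is 0.058 + 0.015 + 0.030 + 0.033 = 0.136. At 40% it is 0.317 + 0.133 + 0.196 + 0.140 = 0.787 (terms rounded).

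| True rate | 10% | 15% | 20% | 25% | 30% | 40% | 50% |
|---|---|---|---|---|---|---|---|
| Count reached | 1% | 5% | 14% | 28% | 46% | 79% | 95% |

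Patients 21 to 25 are covered only by the death trigger. Adding 9 of 25 would move 14% to 14.2% and 79% to 82%.

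**4. Sensitivity to the acceptable rate.** Section 2.2 gives two discontinuation rates from the 173-patient trial. They are not grade 3 or higher rates, but they show how the counts move under the same criterion. At 13.2% (abnormal laboratory values) the counts are 3/5, 4/10, 5/15, 6/20. At 24.8% (adverse events or progression) they are 4/5, 5/10, 7/15, 8/20.

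**5. Timing.** The documents give neither accrual speed nor event times. Assumptions for a simulation: evenly spaced accrual at 1, 2 or 4 patients a month; treatment for 6 months (all stop as non-responders) or 12 months (the maximum); event times uniform from first dose to 30 days after planned last dose. Chance that a count is reached before all 25 are enrolled:

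| True rate, treatment | 1/month | 2/month | 4/month |
|---|---|---|---|
| 40%, 6 months | 77% | 65% | 26% |
| 40%, 12 months | 67% | 31% | 4% |
| 30%, 6 months | 44% | 34% | 12% |
| 30%, 12 months | 36% | 14% | 2% |

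**6. Who could still benefit.** Section 2.2 gives 45% discontinuation in year 1. Assumed exponential, this is −ln(0.55)/12 = 0.050 per month. When a count is reached, the mean number of patients not yet started, or still on drug without an event, is about 11 to 15 of 25 over the twelve cells of step 5.

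**The case against.** The strongest reply is that the choice is open and the substitute is real: a DSMB with power to hold or terminate, weekly PI review, 24-hour SAE reporting and annual DSMC review. The drug is FDA-approved. Entry limits on creatinine (1.5 × ULN) are tighter than the contraindication (2 × ULN), and patients with platelets at or below 50,000 are excluded. Nothing bars an unscheduled DSMB meeting, and a trigger could sit in the institutional monitoring plan, which could not be checked. All of this stands, and it limits the point to an improvement.

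It is also fair that the 20% is assumed and moves the counts (step 4), and that the yield is modest. With 4 patients a month and 12 months of treatment, the count seldom precedes full enrolment. The gain of up to 6 months applies only if the PI would not call the DSMB anyway.

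A reader might draw stronger conclusions that the documents do not support:

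- **That patients are unprotected, or that oversight has failed.** The safeguards above exist; what is missing is an obligation.
- **That nearly everyone still within planned treatment would benefit from the earlier review.** That count includes patients who have already had the event and ignores the 45% discontinuation.
- **That a related death is likely enough to put a figure on.** Both deferasirox trials described in Section 2.2, with 28 and 26 deaths, report none as drug related. I therefore give no probability. The case for a death trigger rests on the listed fatal toxicities and the reporting route, not on an estimated rate.

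**Conclusion.** The point holds as a cheap safety improvement to a declared design choice. It covers the supplied documents only.

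The death trigger is the firmest part, because it needs no assumed rate. The counts are provisional until the investigators and DSMB confirm the acceptable rate. At 20%, they catch a true rate of 40% in 79% of trials and 30% in 46%. They also hold enrolment in 28% of trials at a true 25%.

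The benefit is review up to 6 months earlier, while about 11 to 15 patients are unstarted or on drug without an event. That figure applies only when a count is reached, and it depends on the assumed accrual, event timing and discontinuation. With fast accrual few patients are spared from starting, and the gain lies mainly in decisions on continued dosing.

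**What to change.** Keep the statement that no interim analysis is planned, limited to efficacy. Replace the toxicity half of the Section 16 sentence with:

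> Enrolment is held and the DSMB convened ad hoc on any death related or possibly related to deferasirox, or if the number of patients with a related or possibly related grade 3 or higher non-hematologic event (counted if attribution is in doubt), from first dose to 30 days after last dose, reaches 3 of the first 5, 5 of the first 10, 6 of the first 15 or 7 of the first 20 treated patients. The DSMB decides whether to resume, modify or stop, including continued dosing if enrolment is complete.

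The investigators and DSMB confirm 20%, or choose another rate and replace the four counts, before adoption. The wording on doubtful attribution belongs in the rule itself, because Section 8.1 defines related or possibly related as more likely than not, which alone would undercount. The window follows Section 9.4. Section 8.2 starts capture at enrolment, but an event before first dose cannot be due to the drug, so the count is unaffected. Update the count at the weekly PI review, and refer to it in Section 10 where stopping rules are listed.

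Cost: one paragraph, one cross-reference and one decision on the rate, with no new committee, visits or patients. Attribution must be recorded for non-serious grade 3 or higher non-hematologic events, because Section 9.2 requires it only for SAEs. The downside is an unneeded hold in about 14% of trials at a true 20%. Relatedness remains a PI judgement. The 4-of-25 efficacy test is unchanged unless the DSMB stops the trial.
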